A. A tipping point analysis is a type of sensitivity analysis used to assess how robust the results of a study are to potential changes or assumptions, especially in the presence of missing data or uncertain parameters. It identifies the point at which the study’s conclusions would change if certain assumptions or values were adjusted. In the context of missing data, for example, tipping point analysis can determine how much the imputed or missing data would need to shift in order to alter the outcome of the analysis. This helps evaluate the stability of the results and the impact of potential biases on the conclusions.

Q. What are the benefits of adding the propensity score as a covariate when there aren’t enough events to include multiple covariates directly?

A. When you don’t have enough events to directly include multiple covariates in a model, adding the propensity score as a covariate offers several benefits. It reduces dimensionality by summarizing multiple covariates into a single variable, improving model stability and avoiding overfitting. This approach efficiently adjusts for confounders without the need for a large number of parameters, maintaining statistical power and reducing bias in small sample settings. Additionally, it helps avoid multicollinearity and provides flexibility across different types of models, making it a valuable tool when dealing with sparse data.

Reference: Austin PC. An Introduction to Propensity Score Methods for Reducing the Effects of Confounding in Observational Studies. Multivariate Behav Res. 2011 May;46(3):399-424. doi: 10.1080/00273171.2011.568786. Epub 2011 Jun 8. PMID: 21818162; PMCID: PMC3144483.

R Session info

```

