SSO within 6 weeks was analyzed using logistic regression. Separate logistic regression models were fit for the RCT and for the observational cohort, with mesh type (XenMatrix vs. Strattice) as the primary predictor. Simple logistic regression and multivariable logistic regression was used for each study type (RCT and observational). Both models were adjusted by hernia width, CDC wound class, immunosuppression, and recurrent hernia to account for potential confounding in the observational group. Covariates were selected based on evidence in the literature as well as potential imbalance. The final number of covariates was limited to avoid model overfitting.

Confounders:

- Hernia width
- Wound class
- Immunosuppression
- Recurrent hernia

After obtaining separate estimates from the RCT and observational cohort, a random-effects meta-analysis was performed to derive a combined estimate. A combined estimate for the log odds ratio was calculated using inverse variance weighting and a restricted maximum likelihood estimator. Between-study heterogeneity was assessed by the I^2 measure.

Forest plots and summary tables for the log odds ratio and odds ratio were generated to summarize results.

Statistical and Study Design Considerations

Rationale for Combining RCT and Observational Study Data

- RCT was terminated early for difficulties with enrollment, resulting in very imbalanced group sizes.
- While some guidelines caution against combining observational studies with RCTs in a single meta-analysis due to methodological differences [2], other sources emphasize that in many situations, the benefits of incorporating all available evidence can outweigh the drawbacks, provided proper methods are used [2, 3]
- [3] proves a framework for synthesis of non-randomized and randomized studies.
 - In this study, the observational data come from the same single site as the RCT and are not subject to publication bias.

Choice of Statistical Methods

- Frequentist methods were chosen for broader audience familiarity. Although Bayesian multi-level models are an option, they can be sensitive to prior specification, and the intended audience may be less familiar with them.
- There are not enough events to perform analysis for other outcomes.
- Propensity score matching was not used because it can substantially reduce the sample size (i.e., discarding unmatched patients).

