SSO within 6 weeks : Yes	20	4/12 (33.33)	4/8 (50.00)	$\chi^2_1=0.56, P=0.46^2$
SSO Type (cata)				
Skin necrosis : Yes	20	0/12 (0.00)	1/8 (12.50)	$\chi^2_1=1.58, P=0.21^2$
Enterocutaneous fistula : Yes	20	2/12 (16.67)	0/8 (0.00)	$\chi^2_1=1.48, P=0.22^2$

Table 3b: 6-week outcomes, observational patients (*continued*)

Variables	N	Strattice	XenMatrix	Test Statistic
Dehiscence : Yes	20	2/12 (16.67)	0/8 (0.00)	$\chi^2_1=1.48$, P=0.22 ²
Seroma : Yes	20	1/12 (8.33)	0/8 (0.00)	$\chi^2_1=0.70$, P=0.40 ²
Hematoma : Yes	20	0/12 (0.00)	0/8 (0.00)	NA
Infection : Yes	20	1/12 (8.33)	3/8 (37.50)	$\chi^2_1=2.55$, P=0.11 ²
Mesh infection : Yes	19	0/11 (0.00)	0/8 (0.00)	NA

Note:

N is the number of non-missing value. 1 Kruskal-Wallis. 2 Pearson. 3 Wilcoxon.

Stat, P is the test statistic and p-value.

cata = check all that apply

Results

Executive Summary

Unadjusted Random Effects Meta-Analysis (Simple Logistic Regression):

Effect Estimate (Odds Ratio): 3.718 (0.897, 15.404)

Significance: The pooled estimate was not statistically significant.

Heterogeneity:

I^2 (total heterogeneity / total variability): 3.29%

H^2 (total variability / sampling variability): 1.03

Test for Heterogeneity:

$Q(df = 1) = 1.0340$, $p\text{-val} = 0.3092$

There appears to be minimal variability between the two studies. The I^2 value of 3.29% indicates that nearly all of the total variation can be explained by chance rather than true heterogeneity, and an H^2 of 1.03 reflects low excess variability. The Q test ($Q = 1.034$, $p = 0.3092$) is nonsignificant, confirming that there is no strong evidence of meaningful heterogeneity.

Adjusted Random Effects Meta-Analysis (Multivariable Logistic Regression):

Effect Estimate (Odds Ratio): 12.476 (1.745, 89.199)

Significance: The pooled estimate was statistically significant.

Heterogeneity:

I^2 (total heterogeneity / total variability): 0.00%

H^2 (total variability / sampling variability): 1.00

Test for Heterogeneity: $Q(df = 1) = 0.2830$, $p\text{-val} = 0.5947$

There is effectively no evidence of meaningful heterogeneity between the RCT and the observational study, provided by 0.00% I^2 value. Similarly, $H^2 = 1.00$ supports the absence of excess variability beyond what would be expected by sampling error alone. Finally, the Q test ($Q = 0.2830$, $p = 0.5947$) is non-significant, confirming that the studies are consistent and do not exhibit statistically detectable heterogeneity.

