When covariates were included in the model, a previously non-significant association between the exposure and outcome became statistically significant. This shift suggests that the unadjusted analysis may have been confounded—i.e., certain variables were masking or biasing the relationship.

Note

Be wary of exaggerated findings, as smaller studies are more prone to exaggeration. This is known as a Type M (magnitude) error. In other words, a finding must be large enough to exceed the statistical significance threshold despite wide confidence intervals, which systematically inflates the estimated effect size. Consequently, although we observed a strong effect, its true magnitude may be substantially lower than our point estimate suggests.

Gelman, A., & Carlin, J. (2014). Beyond Power Calculations: Assessing Type S (Sign) and Type M (Magnitude) Errors. *Perspectives on Psychological Science*, 9(6), 641-651.

[figure not shown]
Random Effects Meta-Analysis: Simple Logistic Regression

Simple logistic regression = logistic regression with no adjustment for confounders

[figure not shown]
Random Effects Meta-Analysis: Simple Logistic Regression

Study	Estimate (log OR)	95% CI (log OR)	Estimate (OR)	95% CI (OR)	P-value
Randomized	2.162	(0.365, 5.123)	8.684	(1.441, 167.853)	0.049
Observational	0.693	(-1.143, 2.597)	2.000	(0.319, 13.423)	0.459
RE Meta-Analysis	1.313	(-0.108, 2.735)	3.718	(0.897, 15.404)	0.070

Forest Plot: Log Odds Scale

Forest Plot: Odds Scale

[figure not shown]

Random Effects Meta-Analysis: Multivariable logistic regression

[figure not shown]
Random Effects Meta-Analysis: Multivariable Logistic Regression

Study	Estimate (log OR)	95% CI (log OR)	Estimate (OR)	95% CI (OR)	P-value
Randomized	2.968	(0.815, 6.261)	19.458	(2.258, 523.717)	0.023
Observational	1.882	(-0.898, 5.783)	6.569	(0.407, 324.629)	0.230
RE Meta-Analysis	2.524	(0.557, 4.491)	12.476	(1.745, 89.199)	0.012

Log Odds Scale

Odds Scale

FAQ

Q: What is overfitting?

A: Overfitting in regression happens when a model is too complex, often due to too many parameters relative to a small sample size, causing it to capture noise rather than the true data pattern. With limited data, the model lacks sufficient information to generalize well, leading to poor performance on new data because it is overly tailored to the specific quirks of the training set.

Q: What is a chunk (or composite) test?

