A: A chunk or composite hypothesis test is often used for categorical variables to assess whether the entire variable contributes significantly to the model, rather than just specific categories. By testing all categories together, this approach helps determine if the variable as a whole has an effect, rather than focusing on individual category differences alone.

Q: What can I say when I have a large p-value?

A. This is a friendly reminder that absence of evidence does not mean evidence of absence. A large p-value doesn't prove there is no effect; it simply indicates that we don't have strong evidence to detect a difference. Instead of incorrectly concluding "there were no differences," it's more accurate to say, "there was no evidence of a difference." Additionally, you can use the confidence interval to provide more context. For example, if comparing complication rates, and the confidence interval suggests the difference could be as much as ± 5 percentage points, you might say: "If there is a difference between procedure A and procedure B, it is likely no larger than 5 percentage points." Similarly, for odds ratios, if the confidence interval includes a range up to 2, you could say, "There may be at most a 100% increase in odds or up to a 50% decrease in odds." This acknowledges uncertainty without overinterpreting the results.

Answer generously borrowed and adapted from this blog post([link](#)) by [name].

Also see this article for explanation of interpretation of evidence and suggestions about communicating levels of evidence.

Q. What is validation and optimism-corrected statistics?

A. When a model is fit to a dataset, it tends to perform better on that dataset than it would on new, unseen data, leading to overly optimistic predictions and performance statistics. To adjust for this, techniques like cross-validation or bootstrapping are used to correct for this optimism, producing "optimism-corrected" statistics, which provide a more realistic estimate of the model's performance on future data. These corrections help ensure that the model's results are not overly tailored to the training data and are more generalizable.

Q. What are Brier scores (B)?

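### Two studies with 12 and 8 events cannot confirm that the RCT and the cohort agree, and a pooled p-value crossing 0.05 is not evidence of confounding

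*SAP*

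**What the plan says.** The method is stated under Primary Outcome Analysis: "Between-study heterogeneity was assessed by the I^2 measure", with inverse-variance pooling and REML.

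The Executive Summary interprets the unadjusted result (Q 1.0340, p 0.3092, I² 3.29%, H² 1.03) with the sentence "There appears to be minimal variability between the two studies". For the adjusted result (Q 0.2830, p 0.5947, I² 0.00%, H² 1.00) it says that H² "supports the absence of excess variability beyond what would be expected by sampling error alone" and that the non-significant Q is "confirming that the studies are consistent and do not exhibit statistically detectable heterogeneity". The summary gives no interval for the difference between the two studies.

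The pooled odds ratio goes from 3.718 (p 0.070) unadjusted to 12.476 (p 0.012) adjusted. The SAP comments: "This shift suggests that the unadjusted analysis may have been confounded".

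The SAP's own FAQ, on large p-values, reminds the reader that "absence of evidence does not mean evidence of absence". It advises reporting that no evidence of a difference was found, with the confidence interval for context.

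**The concern.** Two conclusions go further than the data allow.

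The first turns a failure to detect a difference into a finding of agreement. This matters because the pooled estimate combines randomised and non-randomised patients, and the SAP itself notes that some guidelines advise against that. A reader who is told that the two sources are consistent will trust the adjusted odds ratio of 12.5 more than the evidence permits.

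The second treats a move from p above 0.05 to p below 0.05 as a pointer to confounding. Significance depends on the estimate and its standard error together, and crossing a threshold says nothing about why the estimate moved. It invites the reading that adjustment uncovered an effect that had been masked.

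**Working it through.** **Inputs.** SSO within 6 weeks: RCT 11/30 XenMatrix v 1/16 Strattice (Table 3a); cohort 4/8 v 4/12 (Table 3b). That is 12 and 8 events. Adjusted log odds ratios and p-values come from the multivariable table: 2.968 (p 0.023) and 1.882 (p 0.230).

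**Reproducing the SAP, unadjusted.**
- RCT: log OR = ln(11×15/(19×1)) = 2.162; variance = 1/11 + 1/19 + 1/1 + 1/15 = 1.210; SE 1.100.
- Cohort: log OR = ln(4×8/(4×4)) = 0.693; variance = 1/4 + 1/4 + 1/4 + 1/8 = 0.875; SE 0.935.
- Difference d = 1.468; SE = √(1.210 + 0.875) = 1.444; Q = (1.468/1.444)² = 1.034, p 0.309.
- REML τ² = (d² − 2.085)/2 = 0.035; pooled OR 3.718 (0.897 to 15.404), p 0.070. All match.

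**Reproducing the SAP, adjusted.** The SEs are recovered from the Wald p-values: 2.968/2.273 = 1.306 and 1.882/1.200 = 1.568. Then d = 1.086, SE = √(1.306² + 1.568²) = 2.040, Q = 0.283 and pooled OR = 12.47. These match within rounding.

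**Three statistics, one piece of information.** With two studies, I² = max(0, (Q − 1)/Q). Unadjusted this is 0.034/1.034 = 3.29%; adjusted, Q is below 1, so I² is 0%. H² equals Q when Q exceeds 1, and is otherwise 1. I² and H² therefore add nothing to a single 1-df test.

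**Ratio of odds ratios, RCT/cohort:** exp(d ± 1.96 × SE).
- Unadjusted: exp(1.468 ± 2.830) = 4.3 (0.26 to 74).
- Adjusted: exp(1.086 ± 3.999) = 3.0 (0.05 to 162).
- Check on the Wald form: a profile-likelihood interval from the four unadjusted proportions is 0.30 to 125. Combining the printed adjusted study intervals by square-and-add gives exp(1.086 − √(2.153² + 3.901²)) to exp(1.086 + √(3.293² + 2.780²)), about 0.03 to 220.

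**Power of Q at two-sided 5% for a true tenfold ratio** (ln 10 = 2.303; illustrative), normal approximation.
- Unadjusted: 2.303/1.444 = 1.595, giving about 36%.
- Adjusted: 2.303/2.040 = 1.129, giving about 20%.
- Full enumeration of the unadjusted test gives 26 to 44%, assuming a Strattice risk of 6.25% or 15% in the RCT and 33% in the cohort, and a cohort odds ratio of 1 or 2.

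**Change on adjustment.**

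| | OR | p |
|---|---|---|
| RCT | 8.7 to 19.5 | 0.049 to 0.023 |
| Cohort | 2.0 to 6.6 | 0.459 to 0.230 |
| Pooled | 3.7 to 12.5 | 0.070 to 0.012 |

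Only the pooled p-value crosses 0.05. Mesh plus four covariates is at least five terms, so there are at most 12/5 = 2.4 and 8/5 = 1.6 events per term. That is few enough for sparse-data inflation. An odds ratio can also rise on adjustment without any confounding, because it is non-collapsible.

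**Covariate imbalance** (Tables 1a to 2b, Strattice v XenMatrix; previous repair is taken as the tabulated counterpart of recurrent hernia).
- Cohort: immunosuppression 4/12 v 0/8, wound class 4 in 3/12 v 0/8, previous repair 7/12 v 3/8. All were more frequent with Strattice. Median imputed hernia width was larger with XenMatrix, 12.45 v 16.50.
- RCT: immunosuppression 2/16 v 10/30 and wound class 4 in 2/16 v 7/30 run the other way; previous repair is about equal (11/16 v 20/30); median imputed width is larger with Strattice, 15.80 v 12.90.

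**Secondary check.** In the unadjusted RCT row, p 0.049 corresponds to a Wald interval of exp(2.162 ± 1.96 × 1.100) = 1.005 to 75.0. The printed interval is "1.441, 167.853". On the log scale it extends 1.797 below the estimate and 2.961 above it, so it comes from another method.

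**The case against.** The strongest reply is that nothing numerical depends on this. REML was used throughout, no step was triggered by Q, and no pooled estimate would change. That stands, and it limits the weight of the point.

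Much of the surrounding wording is also fair. Saying that no strong evidence of heterogeneity was found, or that none was statistically detectable, is acceptable. The H² sentence is close to a description of what H² = 1 means. The unadjusted sentence is softened, and outright consistency is asserted only for the adjusted analysis. What remains unsupported is the claim of consistency and, less sharply, the word minimal.

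The confounding sentence is hedged, and the SAP gives a separate reason for adjusting: small samples and possible imbalance. If the three cohort factors above raise SSO risk, which is an assumption, masking in the cohort is plausible. This too stands, so the criticism is of the reason given and not of adjustment itself.

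The SAP also warns that "its true magnitude may be substantially lower than our point estimate suggests". That caution concerns the size of the effect. It does not address whether the studies agree or why the estimate rose.

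Four stronger readings are tempting, and the documents support none of them:
- That the studies disagree: both intervals for the ratio include 1.
- That confounding is excluded: the cohort tables leave it open.
- That the pooled result rose mainly because the RCT's weight grew from 42% to 59%: the weights account for only 0.18 to 0.25 of the 1.21 rise in pooled log odds ratio, about 15 to 20%.
- That the interval methods are labelled nowhere: the forest plots are not shown, so only the readable tables can be judged.

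**Conclusion.** The point holds as a matter of interpretation and is minor. The heterogeneity statistics are correct, but they do not confirm consistency. The data are compatible with an RCT odds ratio about four times lower or 74 times higher than the cohort's unadjusted, and about 18 times lower or 162 times higher adjusted. The adjusted figures rest on Wald SEs recovered from rounded p-values, and the power figures on a normal approximation and an illustrative tenfold ratio. The alternative intervals are of the same order, so the conclusion does not depend on these choices.

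The pooled p-value moving from 0.070 to 0.012 does not support an inference of confounding. Confounding, non-collapsibility and sparse-data inflation are all possible and cannot be separated with the information given.

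**What to change.** In the Executive Summary:
- Replace the consistency and minimal-variability wording with a statement such as: *no evidence of a difference between the studies was found, but two studies of this size cannot show whether the effects agree.*
- Report the ratio of odds ratios with its interval for both analyses: 4.3 (0.26 to 74) and 3.0 (0.05 to 162).
- Replace the confounding sentence with the changes themselves (RCT 8.7 to 19.5, cohort 2.0 to 6.6, pooled 3.7 to 12.5) and say that the cause cannot be determined.

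Secondary: in the unadjusted study table, take the RCT row's interval and p-value from one method, or label both.

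The cost is a few sentences, one added line of results and a table label. It needs no new data. The report gives up the claim that the two sources agree and the suggestion that adjustment uncovered a masked effect.

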## R version 4.4.1 (2024-06-14)
## Platform: x86_64-apple-darwin20
## Running under: macOS 15.3
##
## Matrix products: default
## BLAS: /Library/Frameworks/R.framework/Versions/4.4-x86_64/Resources/lib/libRblas.0.dylib
## LAPACK: /Library/Frameworks/R.framework/Versions/4.4-x86_64/Resources/lib/libRlapack.dylib; LAPACK version
##
## locale:
## [1] en_US.UTF-8/en_US.UTF-8/en_US.UTF-8/C/en_US.UTF-8/en_US.UTF-8
##
## time zone: America/New_York
## tzcode source: internal
##
## attached base packages:
## [1] stats      graphics   grDevices  utils      datasets   methods    base
##
## other attached packages:
## [1] broom.helpers_1.17.0 broom_1.0.7
## [4] Hmisc_5.2-2         tangram_0.8.2
## [7] R6_2.5.1            ggplot2_3.5.1
## [10] dplyr_1.1.4         here_1.0.1
## [13] kableExtra_1.4.0
##
## loaded via a namespace (and not attached):
## [1] gtable_0.3.6      xfun_0.49
## [5] vctrs_0.6.5       tools_4.4.1
## [9] tibble_3.2.1      cluster_2.1.6
## [13] data.table_1.16.4 checkmate_2.3.2
## [17] stringr_1.5.1     MatrixModels_0.5-3
## [21] snakecase_0.11.1  SparseM_1.84-2
## [25] yaml_2.3.10       htmlTable_2.4.3
## [29] pillar_1.10.0     MASS_7.3-60.2
## [33] nlme_3.1-164     tidyselect_1.2.1
## [37] polspline_1.1.25 stringi_1.8.4
## [41] rprojroot_2.0.4   fastmap_1.2.0
## [45] cli_3.6.3        base64enc_0.1-3
## [49] foreign_0.8-86   withr_3.0.2
## [53] lubridate_1.9.4   timechange_0.3.0
## [57] gridExtra_2.3     zoo_1.8-12
## [61] rlang_1.1.4      glue_1.8.0
## [65] rstudioapi_0.17.1 systemfonts_1.1.0
## To cite R in publications use:
##
## R Core Team (2024). _R: A Language and Environment for Statistical Computing_. R Foundation for Statistical Computing, Vienna, Austria.
## <https://www.R-project.org/>.
##
## A BibTeX entry for LaTeX users is
##
## @Manual{,
##   title = {R: A Language and Environment for Statistical Computing},
##   author = {{R Core Team}},
##   organization = {R Foundation for Statistical Computing},
##   address = {Vienna, Austria},
##   year = {2024},
##   url = {https://www.R-project.org/},
## }
```

```
## We have invested a lot of time and effort in creating R, please cite it
## when using it for data analysis. See also 'citation("pkgname")' for
## citing R packages.
```
